## A. SPECIFIC AIMS

More than 40% of children enrolled in federally funded programs are overweight or obese by age 5. This is concerning because obese children have a 70% chance of becoming obese adults. Unfortunately, extant obesity efforts have had a limited impact among low-income underserved children, in part because of limitations inherent to existing programs: 1) short duration and low intensity; 2) late timing of implementation, when children are already overweight or obese; 3) delivery methods limiting their accessibility and sustainability; and 4) failure to address barriers such as a lack of culturally competent and in-language services, poverty, housing instability, and access to care, which interfere with healthy lifestyle changes. *To address these gaps, we have integrated simple, evidence-based nutrition and physical activity components as part of the services already delivered by our home visitation partner, Healthy Families America, with the long-term goal to deploy these efforts to Home Visitation Programs (HVPs) nationwide.* Annually, over 500 publicly and privately funded HVPs provide nationwide services to more than 650,000 low-income, underserved infants and their families. The home visiting structure is not only an unparalleled model for scalable and sustainable childhood obesity prevention, but it also provides a unique opportunity to understand factors related to the intergenerational transmission of obesity in families who are most at risk.

Over the last four years, our transdisciplinary team of researchers, home visiting stakeholders, families, and community stakeholders (hereafter referred to as the *COPE team*), has integrated evidence-based nutrition and physical activity components into an engaging module that we call **COPE: Childhood Obesity Prevention @ home / Contrarrestar Obesidad: Programa para niños En casa**. COPE is delivered in English and Spanish as an *enhancement module* to the services of our HVP partner. Our pilot work supports the successful integration, feasibility, and preliminary efficacy of COPE.

*The proposed study builds upon the momentum, resources, and research infrastructure of our pilot work to test the larger-scale and sustained impact of COPE on infant's and mothers' obesity outcomes, and to study key mechanisms of maternal and social transmission on infants' obesity risk.* Specifically, 300 low-income mothers/infants enrolled in Healthy Families America HVP will be recruited and enrolled in the study, for an effective final sample of 200 mothers/infants. Based on standard HVP procedures, mothers/infants will be matched to highly trained home visitors (nurses) based on their ethnicity/race and language preferences. Home visitors, in turn, will be randomly assigned to deliver the standard HVP curriculum only or the standard HVP curriculum + COPE as part of their weekly home visits for two years of HVP services. Comprehensive assessments of mothers/infants will be conducted at enrollment and after 6 and 12 months of intervention.

**Specific Aim 1 (maternal and infant outcomes).** Test the direct effects of COPE on infants and mothers' weight, metabolic risks, diet/energy intake, and physical activity. This will be accomplished by comparing changes in body weight, metabolic markers, and eating and activity-related behaviors between infants/mothers across study arms (HVP only vs. HVP+COPE). These results will indicate whether HVP is an effective infrastructure for primary and secondary obesity prevention.

**Specific Aim 2 (maternal transmission).** Test whether breastfeeding and maternal diet and activity, feeding practices, and food insecurity mediate the effect of COPE on infants' outcomes. This aim will test mechanisms of maternal transmission on infants' obesity risks.

**Specific Aim 3 (social transmission).** **Aim 3** is two-pronged. **Aim 3a** tests the direct effect of HVP+COPE (vs. HVP only) on the characteristics of the social and community networks that surround mothers and infants (i.e., the density, composition, and quality of "health support networks"). **Aim 3b** tests whether the characteristics of social networks mediate the effects of COPE on maternal and infant outcomes. These findings will indicate if HVP obesity prevention efforts can alter and/or activate social network mechanisms.

**Secondary Aim.** Conduct a real-life economic analysis (costs, cost-savings, and non-monetary benefits) of integrating COPE into existing HVPs.

This proposal addresses the impetus to develop interventions targeting at-risk infants before obesity is established. Although maternal-infant interventions are much-needed, they present implementation and dissemination challenges, including limitations on compliance and retention, and limited potential for scalability and sustainability. Our proposed strategy overcomes these challenges through an innovative solution that merges evidence-based nutrition and activity components into an existing, ongoing federally-funded infrastructure. *The proposed research is timely as the Institute of Medicine, the United States Department of Agriculture (USDA), and Health and Human Services (DHHS) extend their recommendations to address key factors influencing obesity risk in children from birth to 24 months of age.*

[figure not shown]

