
**C.3. Participants.** Participants will be low-income mothers/infants (6mo at enrollment) *who are already receiving services from our HVP partner (Figure 6)*. Thus, study enrollment does not require that we recruit more families than our HVP partner is already enrolling. Mothers are enrolled in HVP services through outreach and screening pre-partum, in English or Spanish, at community health centers and hospitals. In order to be eligible mothers must meet a number of (but not all) risk criteria (e.g., low-income, housing instability). Enrolled mothers are matched to a home visitor (nurse) based on culture and language. **Recruitment.** Assessment workers (distinct from home visitors delivering services) who enroll families into services will introduce the study to mothers and obtain written consent. They will clarify with mothers that their refusal to participate in the study will not affect their receipt of any other services provided by the HVP. In our experience, families feel comfortable refusing if they are not willing to participate. Mothers/infants will be ineligible if they have any of the following conditions: eating disorders (e.g., bulimia nervosa), schizophrenia, and obesity-related syndrome (e.g., Prader Willi). Participants enrolled in a weight-loss program will be ineligible. Based on our pilot work, we expect to recruit 70% Hispanic/Latino, 13% African American, 8% White, 5% American Indian/Alaskan, 4% mixed race. **Retention.** We have learned a great deal about retention through our pilot work. For instance, most attrition from HVP services occurs in the first six months of services. Therefore, to maximize retention, mothers will be invited to participate in the study *after six months of home visits*. The unique relationship between home visitors and mothers facilitates subsequent retention, as many of these mothers are socially isolated and home visitors are important confidants and supports. We will use multiple strategies that are effective for high-risk populations to further retain the study sample: (1) gift cards of \$25 at each data collection, with all incentives paid after each assessment; (2) frequent contacts to maintain engagement and foster open communication; (3) quarterly newsletters to update subjects about study activities; (4) acknowledging birthdays and milestones; (5) reminder phone calls the day before the weekly visits and assessment sessions. **Randomization.** Randomization will be at the level of home visitors, who deliver the HVP (cluster randomization). Home visitors who serve mothers that are participating in the proposed study will be randomly assigned to deliver either HVP only or HVP+COPE. Potential concerns with randomizing by home visitors are feasibly addressed in this study. First, the likelihood of

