**1. Maternal nutrition.** Home visitors teach mothers to prepare and store foods they receive from *WIC* and the *Food Bank*, and to gradually build healthier nutrition and activity goals congruent to their cultural practices and ethnic specific food palate: (a) increasing intake of vegetables and fruits (≥5 servings/day of fruits and vegetables) and integrating nutrient-dense ingredients in their families’ meals/recipes; (b) limiting intake of high-saturated fat and sugar in modifying families’ favorite recipes (the material is adapted to families’ cultural and personal preferences); (c) eliminating sugar-sweetened beverage intake, supported by the provision of information and activities on sugar content, long-term effects of high sugar consumption, importance of drinking water, and impact of advertising; (d) teaching healthy portion sizes using different visual activities. **2. Infants/young children nutrition.** The curriculum promotes sustained breastfeeding for the first two years and the gradual integration of complementary feeding (pureed and age-appropriate solid foods) that support healthy eating for infants. Mothers learn about feeding/eating developmental stages and transitions, and healthy feeding practices to promote: (a) responsiveness to child hunger and fullness cues; (b) the consumption of nutrient-dense foods (as opposed to energy-dense); (d) the transition to structured schedule for meals/snacks from complementary feeding; and (d) the use of non-food related child soothing techniques. Mothers also learn strategies to address neophobia, such as repeated multi-sensory (i.e., smell, touch, taste) exposures to nutrient-dense novel foods, gradual texture shaping, parents/caregivers modeling, and involvement of children in food selection and preparation; and strategies to handle meal-related tantrums (e.g., redirection, positive reinforcement of appropriate behaviors). **3. Maternal/child physical activity.** Although there is no unequivocally accepted guidelines for the number of minutes children 0-2yo should be active each day, the DHHS has summarized recommendations from the National Association for Sport and Physical Education, the American College of Sports Medicine, and the National Institutes of Health: (a) daily planned physical activities, including tummy time, that safely support the infant’s developmental milestones (e.g. head and neck self-support, rolling, floor sitting, kicking, crawling, reaching and grasping for objects, etc.); (b) engage in 30

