**C.5. Measurements.** HVP *Assessment Workers* (registered nurses who can draw blood) who enroll families into standard HVP services, have been trained to screen and recruit eligible families for the proposed project. They will administer the assessments (English or Spanish; **Table 6**) in the families’ homes or at the HVP clinic (as needed) at baseline/enrollment, and after 6mo and 12mo of services. *Home visitors* will be trained to gather interim (objective) weight measurements for the purpose of generating more frequent data points, triangulated with the assessment workers’ measurements.

**Medical and family history.** A thorough family history and physical examination will be conducted at baseline. We will collect demographic data, including socioeconomic status (education, income, eligibility for SNAP).

**Infant growth & waist trajectories.** Weight will be measured on a digital scale (Tanita) accurate to the nearest 5g. Length will be measured to the nearest 0.1 cm using an infanto-meter using the standardized WHO approach,

Table 6. Assessment time points (month of intervention) and key measures							
	Baseline	3	6	9	12	15	18
COVARIATES							
Demographics, household composition, medical history, post-partum depression, activity readiness	X						
MOTHERS							
Weight/height, waist circumference	X	X	X	X	X	X	X
Blood and vitals	X						X
24h diet & activity recall	X		X				X
Feeding and food insecurity	X		X				X
Social support and networks	X		X				X
Home environment	X		X				X
INFANTS							
Weight/length, waist circumference	X	X	X	X	X	X	X
Blood (finger prick)	X						X
24h diet & activity recall (from mother)	X		X				X

including use of staff training modules. Weight and length will be used to calculate weight-for-length and weight-for-age z-scores (WHO Standards), as recommended by the CDC for children <24 mos. Infant growth rates will be examined as the change in WLZ from baseline to follow up (12mo) Waist circumference will be measured at the umbilicus (nearest 1-mm) using a non-stretch measuring tape.

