**Infant diet & activity.** To fully capture *infants' diet* (e.g., breastfeeding, use of formula, fruits/vegetables, fat/sugar intake), we will use multiple tools. *Diet recall.* Mothers will be interviewed about their *infants' intake* of fruits, vegetables, friend foods, and sugared beverages. Mothers will complete items from the *Diet and Behavior Questionnaire (DBQ)* of the National Health and Nutrition Examination Survey to capture breastfeeding/feeding history and introduction to

formula and solid foods. *Infants' activity.* Because of validity issues related to accelerometry in infants/young children, we opted to capture time engaged in sedentary activities and structured/unstructured physical activity. Mothers will report their child's activities (e.g., tummy time,)

**Infants and maternal biomarkers for metabolic risks.** Blood will be drawn at the Antelope Valley Partners for Health office by Assessment workers with phlebotomy certification, at baseline for mothers only. *Mothers:* Blood will be drawn by Assessment Workers who will make a maximum of 3 attempts to draw the blood during the first visit. If the first attempt is not successful, mothers will be invited to return on another day for a second (and final) attempt. Plasma will be stored at -70°C for analysis. Biomarkers of type 2 diabetes risk, lipids, and inflammatory markers. CRP will be measured using the Millipore Multiple assay kit at the USC DORI Core Laboratory. Lipids will be assayed using Vitros Colorimetric assays (Johnson & Johnson Clinical Dinostics Rochester, NY) for cholesterol, triglycerides and HDL-cholesterol. Sitting blood pressure (mothers) using auscultation and heart rate will be measured on the right arm after a 5-minute rest. Three readings of blood pressure and heart rate will be obtained and the average of the last two last will be recorded.

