**Aim 1 (maternal/infant outcomes).** Change in weight-related outcomes over the 2-year implementation is the primary outcome comparison. We will use multilevel regression models adjusting for clustering effect of home visitors to compare differences in the main outcomes across time by intervention arm. Regression model can be treated as a special case of path model without mediators. These regression models will include all participants, who have at least 2 measurements, regardless of when the measurements are taken, increasing the follow-up of study participants and statistical power. Specific measures relevant to Aim 1 are maternal and children weight-related measures. These models will allow the evaluation of intervention effects on, for example, child growth trajectory and activity, and mother BMI, metabolic, and behavior outcomes. Investigation of the main effects of COPE on outcomes will be conducted at each follow-up. Baseline outcome measures will be treated as covariates to control for potential

baseline differences. Effects of COPE will be evaluated first at each follow-up assessment point. Longitudinal analyses with all follow-up points (6 and 12 months) will then be conducted to examine profiles across time to investigate the effects of program conditions on trends of outcome measures.

**Aim 2 (maternal transmission).** To estimate the mediational effects of maternal transmission, multilevel path models will be developed and evaluated per our hypotheses. The model specification will be guided by our conceptual model treating Intervention program as the distal variables along with demographic variables to affect mother's weight, diet and behavior as mediators, which in turn may influence infants' outcome. While the intervention program will be at the Level-2 unit, all other variables included in the multilevel path models will be Level-1 variables obtained from mothers and children. Using breastfeeding and maternal diet on infants' weight trajectories as an example, the mediation mechanism of maternal transmission can be expressed by the process: COPE → breastfeeding \* maternal diet → weight. The path model will allow the test of both the direct effect of COPE on infant weight trajectory and its indirect effect on through breastfeeding and maternal diet.

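### Aim 2 leaves the breastfeeding mediator undefined and unadjusted for feeding before entry at 6 months, so a mediator built from feeding history would include feeding that COPE may not be able to change

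*Combined protocol and SAP*

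**What the plan says.** - **Aim.** Section A, Specific Aim 2: "Test whether breastfeeding and maternal diet and activity, feeding practices, and food insecurity mediate the effect of COPE on" infant outcomes.
- **Model.** Section C.6, Aim 2, illustrates the mediation with a path from COPE through breastfeeding and maternal diet to infant weight: "The path model will allow the test of both the direct effect of COPE on infant weight trajectory and its indirect effect" through those two variables.
- **Age at entry.** Section C.3: "Participants will be low-income mothers/infants (6mo at enrollment". Mothers are already HVP clients and are invited after six months of visits.
- **Clock.** Section A: "Comprehensive assessments of mothers/infants will be conducted at enrollment and after 6 and 12 months of intervention". In C.5, the table title is "Table 6. Assessment time points (month of intervention) and key measures". Section C.1 counts months of services instead.
- **Measure.** Section C.5, Infant diet & activity, takes items from an NHANES questionnaire (DBQ) "to capture breastfeeding/feeding history and introduction to" formula and solid foods. It also says that several tools will capture infant diet, with breastfeeding as one example, but the listed recall foods do not include it.
- **Intervention content.** Section C.4: "The curriculum promotes sustained breastfeeding for the first two years and the gradual integration of complementary feeding". Table 4 marks breastfeeding for both HVP and COPE.
- **Adjustment.** Section C.6 treats baseline outcome values as covariates (Aim 1) and lists general covariates, none of which is infant feeding. Factors that differ at baseline will be adjusted for.

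**The concern.** A mediator must be something that the intervention can move. By 6 months of age, initiation, exclusivity in the first half-year and, for some mothers, stopping or first formula are already settled. If COPE begins at enrolment, none of these can lie on its causal path. The plan does not say whether the mediator is ever-breastfed, exclusivity, duration or current status, and it does not separate feeding before and after entry.

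This matters in three ways. A variable made only of pre-entry events tests nothing about COPE. A variable that mixes the two periods adds noise to the link from COPE to breastfeeding. Pre-entry feeding can also influence both later breastfeeding and later weight, so leaving it out of the outcome equation confounds the link from mediator to outcome. A null could be reported as evidence that breastfeeding is not a pathway, or a chance imbalance as evidence that it is.

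**Working it through.** **1. The plan's own figure.** The only numeric power given for the path models is .83 to .93 (C.6, Power Analysis: RMSEA .00 against .08, 10 to 15 degrees of freedom, alpha .05, N=300). The noncentrality is (N-1) x df x 0.08². At N=300 this is 299 x 10 x .0064 = 19.1 and 299 x 15 x .0064 = 28.7, with power .873 and .957. At the planned final N=200 the power is .672 and .808. The stated range does not reproduce at N=300, but that is a separate matter: it concerns overall model fit. No power is given for the breastfeeding indirect effect.

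**2. What COPE can change, by candidate definition (COPE starting at enrolment).**
- Ever breastfed, or formula or solids introduced before 6 months: fixed at entry, so the part that COPE can cause is zero.
- Total duration = pre-entry months + post-entry months. Randomisation makes the expected arm difference in pre-entry months zero, so the expected difference in the total equals the post-entry difference. Only the variance rises.
- Any breastfeeding at follow-up, or months continued since baseline: can change, among mothers still breastfeeding at entry.

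**3. Chance imbalance in pre-entry feeding.** Take N=200 with equal arms, and assume that the plan's inflation factors of 1.4 and 1.8 apply to pre-entry feeding. The standard error of the arm difference, in SD units, is sqrt(4 x 1.4/200) = 0.17 to sqrt(4 x 1.8/200) = 0.19. This is random error, not bias, but it enters the mediator unless adjusted for.

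**4. Size of the COPE-to-breastfeeding link.** Let p be the share still breastfeeding at entry (not in the documents; assumed 20% to 50%, with 100% for reference). Assume that no mother restarts. A 10-point gain in continuation gives .20 x 10 = 2 to .50 x 10 = 5 points over all mothers; a 20-point gain gives 4 to 10.

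For power, assume continuation c of 50% against 70%, with n = 100/1.4 or 100/1.8 per arm and two-sided alpha .05. Power = Φ(p x 0.20/SE - 1.96). Unadjusted, SE² is the sum over arms of pc(1-pc)/n. Stratified on baseline status, it is the sum of p x c(1-c)/n. At p=.5 the variance sums are .1875 + .2275 = .415 and .125 + .105 = .230. At p=.2 they are .0900 + .1204 = .2104 and .050 + .042 = .092.

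| p | Difference, all mothers | Power unadjusted (1.4 / 1.8) | Power stratified (1.4 / 1.8) |
|---|---|---|---|
| 100% | 20 points | 70% / 59% | 70% / 59% |
| 50% | 10 points | 26% / 21% | 42% / 34% |
| 20% | 4 points | 11% / 10% | 20% / 16% |

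A pooled-variance formula changes the unadjusted column by less than 2 points. With 50% against 60% continuation, unadjusted power on that formula is 10% / 9% at p=50% and 6% / 5% at p=20%.

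Restricting to mothers breastfeeding at baseline gives the same power as stratifying, because 0.20/sqrt(v/(pn)) = p x 0.20/sqrt(pv/n). Stratifying also keeps every randomised mother. These figures cover only one of the two links that an indirect effect needs.

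**The case against.** The strongest reply is that the plan never says the mediator is lifetime history. COPE aims at breastfeeding up to two years, several tools are promised for infant diet, and Table 6 marks the feeding and infant diet rows at baseline and follow-up. Breastfeeding after entry is therefore a natural reading. This stands: the defect is an undefined mediator, not a wrong one.

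A reader might infer that a null result is built in, or that any history variable pulls the arm difference toward zero. The documents do not support either. Total duration is not diluted in expectation (step 2). The factor p is not an artefact; it gives the average effect in the enrolled population, which is what the plan's intention-to-treat rule targets. If few mothers can respond, a small overall effect is the right answer. A reader might also infer that the path should be confined to mothers breastfeeding at baseline. That answers a different question, and at p of 20% to 50% it leaves 40 to 100 of 200 mothers across 30 visitors, about 1 to 3 each.

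The plan also promises adjustment for factors found to differ at baseline, and baseline infant weight would absorb part of the influence of pre-entry feeding. This helps, but the first depends on a test result and neither defines the mediator.

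Finally, the start of COPE is unsettled. Visitors are randomised, services begin before birth, and section A has visitors delivering COPE over two years of services. If some mothers receive COPE before enrolment, pre-entry feeding is partly its effect, and adjusting for it would remove real effect. This stands as a condition on the fix.

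**Conclusion.** The point holds in a limited form. As written, the lead example of Aim 2 has no defined breastfeeding variable, its only named items describe history, and no adjustment for the mediator's baseline value is specified. A mediator built from those items could include feeding that preceded COPE: no causal content for ever-breastfed status or introductions before 6 months, and extra variance plus chance imbalance for total duration.

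The size cannot be fixed from the documents. It rests on the share still breastfeeding at 6 months and on the continuation effect, both assumed here, and on COPE starting at enrolment. The contrast may be narrower still because both curricula cover breastfeeding and section B.6 credits home visiting itself with improving it. The point concerns breastfeeding only, not the other Aim 2 mediators, and does not show that Aim 2 must return a null.

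**What to change.** 1. **Reconcile the start of COPE** relative to enrolment across section A, C.1, C.3 and Table 6 in C.5, which count months of intervention or of services and give different durations. The covariates in item 3 are valid only if COPE starts at baseline.
2. **Define the mediator** in C.6, Aim 2, as breastfeeding after enrolment: any breastfeeding at the 6-month assessment, or months continued since baseline. Name one of these in advance and analyse all mothers under intention to treat.
3. **Adjust** the mediator and outcome equations for baseline breastfeeding status and pre-entry feeding history (duration to baseline, age at first formula and at first solids).
4. **Report mothers breastfeeding at baseline** as a sensitivity analysis only.
5. **State the limit:** initiation and early exclusivity cannot be tested as pathways in this trial.
6. **Confirm** that the DBQ items are given at baseline and follow-up. Table 6 has no row that names them.

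The cost is mainly analysis-plan wording, slightly more analysis work and a narrower stated conclusion for the breastfeeding path. If the items are not repeated at follow-up, a current-breastfeeding question would have to be added at those visits.
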